6.4 PARTICIPANT DISCONTINUATION/WITHDRAWAL FROM THE STUDY

Participants are free to withdraw from participation in the study at any time upon request.

An investigator may discontinue or withdraw a participant from the study for the following reasons:

- Pregnancy
- Significant study intervention non-compliance
- If any clinical adverse event (AE), laboratory abnormality, or other medical condition or situation occurs such that continued participation in the study would not be in the best interest of the participant
- Disease progression which requires discontinuation of the study intervention
- If the participant meets an exclusion criterion (either newly developed or not previously recognized) that precludes further study participation
- Participant should be withdrawn from the study if they start on a new drug or receive antibiotics

The reason for participant discontinuation or withdrawal from the study will be recorded on a Case Report Form (CRF). Participants who sign the informed consent form but do not receive the study intervention may be replaced. Participants who sign the informed consent form, receive the study intervention, and subsequently withdraw, or are withdrawn or discontinued from the study, will not be replaced.

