2.2 RISK/BENEFIT ASSESSMENT

Immediate risks:

There are no predicted risks associated with this product. However, some people may experience adverse reactions when trying a new product. NuBest Tall Protein contains milk-based ingredients, so it is not suggested for those with a dairy allergy. It does not contain soy, grain, wheat, GMO, or gluten.

As dairy can interact with a number of medications, all medications should be separated by a minimum of 4 hours from taking the test product.

Long-term risks:

There are no predicted long-term risks related to using this product. Any short-term risk should dissipate after discontinuing the test product.

Immediate benefits:

Participants may experience positive changes in overall health. Also, participants might experience increased energy levels, immune function, and overall well-being.

Long-term benefits:

Participants may experience an increase in height, maintenance of a healthy weight, and enhanced quality of life due to an increase in overall health.

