5.2 EXCLUSION CRITERIA

An individual who meets the following criteria will be excluded from participation in this study:

- 1. Any child with a history of endocrine disorder, heart disease, lung disease, kidney disease, digestive disease or skeletal dysplasia.
- 2. Any pre-existing chronic conditions that would prevent participants from adhering to the protocol, including oncological and psychiatric disorders.
- 3. Is undergoing or planning to undergo significant medical procedures in the next six months.
- 4. A history of severe allergic reactions, including but not limited to any of the product's ingredients.
- 5. Any child with a dairy allergy or lactose intolerance.
- 6. Has undergone any surgeries or invasive treatments in the last six months.
- 7. Has had any major illness in the last three months.
- 8. Having any planned invasive medical procedures during the study period
- 9. Currently participating in any other clinical study.
- 10. Unwilling to follow the study protocol.
- 11. Any child diagnosed with attention-deficit disorder (ADD) or attention-deficit hyperactivity disorder (ADHD).
- 12. Any child currently taking, or have they taken in the last 3 months, any prescription medication targeting ADD or ADHD (such as Adderall, Concerta, Focalin, Evekeo, or Ritalin).
- 13. Any child that is a 'fussy' eater or who the parent suspects may not tolerate consuming the test product daily for six months.

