6.2 INTERVENTION FORMULATION

Intervention Product: Protein, Vitamin A, Vitamin C, Vitamin D, Vitamin E, Thiamine, Riboflavin, Niacin, Vitamin B6, Folate, Vitamin B12, Biotin, Pantothenic Acid, Choline, Calcium, Iron, Phosphorus, Iodine, Magnesium, Zinc, Selenium, Copper, Chloride, Sodium, Potassium, Organic Flax Seed Powder, L-Taurine, Inositol Hexanicotinate, L-Arginine, Bacillus subtilis DE111® Complex (1 Billion CFU) (Probiotic), Eucommia Bark Extract, Vitamin K, Whey Protein Concentrate, Chocolate Bean Powder Processed with Alkali, Organic Evaporated Cane Sugar, Milk Protein Concentrate, Guar Gum Powder, Natural Flavor, Potassium Chloride, Silicon Dioxide, Rebaudioside A (from Stevia Leaf Extract), Sucralose.

Placebo Product Ingredients: Maltodextrin, Guar gum powder, Silicon dioxide, Cocoa powder, Natural creamy vanilla flavor, Organic evaporated cane sugar, Stevia leaf extract, and Sucralose.

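### Section 6.4 provides for leaving the study but not for stopping the product and staying in follow-up, so scores that Section 7's intent-to-treat aim needs may never be collected

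*Combined protocol and SAP*

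**What the plan says.** Section 6.4 opens its list with "An investigator may discontinue or withdraw a participant from the study for the following reasons". The object is the study, not the product. The reasons include significant non-compliance, an adverse event, and "If the participant meets an exclusion criterion (either newly developed or not previously recognized) that precludes further study participation". A disease course that requires the product to be stopped is itself listed as a reason for leaving the study. The last bullet differs in force: a child who begins a new drug or is given antibiotics should be withdrawn. Treated children who leave are not replaced. What is kept is the cause: "The reason for participant discontinuation or withdrawal from the study will be recorded on a Case Report Form (CRF").

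Section 5.2 excludes "Any child with a dairy allergy or lactose intolerance", digestive disease, and any fussy eater or child "who the parent suspects may not tolerate consuming the test product daily for six months". Section 2.2 notes that "NuBest Tall Protein contains milk-based ingredients, so it is not suggested for those with a dairy allergy". In Section 6.2 the test powder lists whey protein concentrate and "Milk Protein Concentrate, Guar Gum Powder, Natural Flavor". The placebo list ("Placebo Product Ingredients: Maltodextrin, Guar gum powder, Silicon dioxide, Cocoa powder", then flavour, sugar and sweeteners) has no milk ingredient. Section 6.1 lets both arms mix the powder with water, milk or smoothies.

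Section 3 makes digestive health and immune function (a count of illnesses) secondary endpoints. Questionnaires run at Baseline and monthly to Month 6; cognition is tested only at Baseline and Month 6. Section 7 commits to intent-to-treat with every randomized child included, whatever the adherence. It gives no method for missing scores.

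**The concern.** Intent-to-treat says whose scores are compared. It cannot supply a score that nobody collected. Section 7 wants to know how the product performs in ordinary use, where some children stop taking it. Section 6.4 allows those children, the non-compliant among them, to be removed from follow-up altogether. The two sections pull against each other.

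The loss need not be random. Antibiotics usually mean an illness, and illness is counted as an endpoint. Digestive upset can bring an unrecognized lactose intolerance to light, and digestion is an endpoint. The dairy in the test powder gives a reason why this second route could be used more often in the active arm. In either case a child may leave because of the outcome being measured, and the questionnaire that would have shown it falls after the exit. Scores not collected during the study cannot be recovered afterwards.

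**Working it through.** **1. What is lost, by time of exit.** From the schedule in Sections 3 and 6.1:

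- Exit before Month 1: no post-baseline questionnaire score at all.
- Exit between two months: earlier scores remain, but the event that caused the exit falls before the next questionnaire and goes unreported there.
- Exit at any time before Month 6: no post-baseline cognitive score, so nothing on the primary endpoint.

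**2. Size of the shift.** The documents give no withdrawal rate and no SD, so there is no plan figure to reproduce and the inputs below are assumptions. Only 30 per arm comes from the protocol (Section 5.4). Let wa and wp be the leavers on active and placebo, and d how much worse leavers would score than stayers at the analysed time point, in within-arm SDs. If leavers were followed, d would be measured off product. Dropping them raises an arm's mean by w × d / 30, so the difference shifts toward the product by

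b = (wa − wp) × d / 30.

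The standard error with leavers missing is SE_obs = sqrt(1/(30 − wa) + 1/(30 − wp)).

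| wa | wp | d | b (SD) |
|---|---|---|---|
| 3 | 0 | 1.5 | 3 × 1.5 / 30 = 0.150 |
| 3 | 0 | 0.75 | 3 × 0.75 / 30 = 0.075 |
| 1 | 0 | 1.0 | 1 × 1.0 / 30 = 0.033 |
| 3 | 3 | 1.5 | 0 |
| 3 | 0 | 0 | 0 |
| 0 | 3 | 1.5 | −0.150 |

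The second row also stands for earlier monthly scores recovering half of a 1.5 SD deficit. The fifth row is the case where symptoms have cleared by Month 6.

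**3. Consequence in the largest case, if the deficit persists off product.** For 3 against 0 with d = 1.5, SE_obs = sqrt(1/27 + 1/30) = 0.2653, and b is 0.150 / 0.2653 = 0.57 SE. With all scores collected, the active-arm variance is 1 + 0.1 × 0.9 × 1.5² = 1.2025, so SE_all = sqrt(1.2025/30 + 1/30) = 0.2710. Assume a two-sided 5% test.

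- (A) The product harms those three children and has no other effect. The true difference is −0.150 and the observed one is 0. The chance of a significant result for the product is 2.5% instead of 1 − Φ(1.96 + 0.150/0.2710) = 0.6%. The harm is hidden.
- (B) The true difference over all randomized children is exactly zero. That chance is 1 − Φ(1.96 − 0.57) = 8.2% instead of 2.5%.

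For one leaver with d = 1, (A) goes from 1.8% to 2.5% and (B) from 2.5% to 3.3%. With d = 0 both stay at 2.5%, however many leave.

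**4. Illness route.** The same formula applies with no presumption about direction. If the product has no effect on illness, equal numbers are expected to leave and b is expected to be 0. If it prevents illness, more placebo children leave and the shift goes against the product (last row).

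**5. Cognition.** If leavers do not differ cognitively, the loss is one of precision. Without leavers the SE is sqrt(2/30) = 0.2582; with three missing it is 0.2653, and 0.2653 / 0.2582 = 1.03, about 3% wider.

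**6. Percentage improved.** Intent-to-treat fixes the denominator at 30 per arm. How a missing Month 6 score is classed is open, and each such child moves the arm's figure by 1/30 = 3.3 percentage points.

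**The case against.** The strongest reply is that the dairy route is narrow. Withdrawal there is discretionary and limited to a criterion that rules out further participation. Known intolerance, digestive disease and suspected poor tolerance are screened out. Milk is an allowed mixer in both arms, and the powder's lactose content is not given, so the added exposure may be small. The event itself still reaches adverse event review (Section 1.3) and the CRF. All of this stands. It lowers the expected number and imbalance but does not restore a missing score.

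A second reply concerns size. Section 2.2 expects short-term effects to disappear once the product is stopped. If so, a leaver followed to Month 6 would score much like the others and the Month 6 shift is near zero. This also stands. The larger figures above need a deficit that lasts off product.

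A reader might infer that the active arm will lose more children, that the digestion result will favour the product, or that its false-positive chance is 8.2%. The documents do not support this: they give no rate of intolerance, no use of milk by arm and no sign that symptoms persist. A reader might also infer bias in the primary cognitive comparison. Nothing in the documents suggests that dairy-intolerant leavers differ in cognition; what is shown is lost data.

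The dairy bullet is also not the strongest instance. The directive on new drugs and antibiotics in the same list leaves less discretion and bears on the illness count.

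**Conclusion.** The gap is definite: Section 6.4 provides only for leaving the study, no assessment follows, and this works against Section 7's stated aim. Its size is unknown and may be zero. For digestion at Month 6 the illustrated range runs from 0, if symptoms clear or leavers are balanced, to 0.15 SD under three assumptions together: three active leavers, none on placebo, and a 1.5 SD deficit that persists off product. For the illness count the direction is open. For cognition only a loss of precision is shown.

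The case for change rests on the conflict between the two sections and on the low cost of removing it, not on a demonstrated bias. The change should be made, and made while scores can still be collected.

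**What to change.** **Section 6.4.** Separate stopping the product from leaving the study, for every listed reason, including antibiotics and non-compliance. The safety decision to stop the product is unchanged. Unless the parent withdraws consent, collect the existing questionnaire at the time of stopping, then the remaining scheduled questionnaires and height and weight measurements, and the Month 6 cognitive tests.

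**Section 7.**

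- Analyse all scheduled scores by randomized arm, whether or not the child is still on product.
- Report the stopping questionnaire separately. Entering it at the nearest month could give a child two scores for one month, or place an early stop at Baseline.
- Keep all randomized children in the percentage-improved denominator. For digestion, count a child who stopped for dairy or digestive intolerance as not improved, whether or not a later score exists. Otherwise a child who recovered after stopping could count as a success for the product.
- Report product stops, reasons and missing scores by arm. The class of a Month 6 score missing for any other reason also needs to be stated in advance; this point does not settle it.

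**Cost.** No new instrument. Per child concerned, at most one stopping questionnaire, the six scheduled ones, three height and weight measurements with devices the family already has, and one cognitive session. The downside is slight burden for a few families and a possibly less favourable digestion result. Some parents will decline, so some scores will still be missing.

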3 OBJECTIVES AND ENDPOINTS

OBJECTIVES	ENDPOINTS	TIMEPOINTS	ASSESSED BY	JUSTIFICATION FOR ENDPOINTS
Primary				
To examine the effect of the NuBest Tall Growth Protein Powder cognitive function.	Improvement in score on assessments: • Double Trouble • Feature Match • Grammatical Reasoning • Digit Span • Token Search	Baseline and Month 6	Cognitive Battery Testing	The combination of these cognitive assessments will provide objective data on the efficacy of the product in improving specific domains of cognitive function.
Secondary				
	Increase in height			

	Maintenance of a healthy weight	Baseline, Month 2, Month 4, Month 6 (height & weight measurements)	Height measured using an Ultrasonic Height	
To investigate the impact of the NuBest Tall Growth Protein Powder on a range of health parameters, including height, weight, energy levels, immune function, and digestion.	Increase energy levels		Measuring Stadiometer	The combination of objective measurements and questionnaires will provide both independent and participant perception data on secondary health parameters.
	Improved signs of digestive health		Weight measured using a FitBit Smart Scale.	
	Increased immune	Baseline, Month 1, Month 2, Month 3, Month 4, Month 5, Month 6.		
	function (assessed via the number of times the child has been ill in the past 6 months)		Study-specific questionnaires	

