6 STUDY INTERVENTION

6.1 STUDY INTERVENTION

- Potential participants (parents + child) who meet the initial inclusion and exclusion criteria can participate in this trial
- If participants meet the inclusion and exclusion criteria after the parents have signed the informed consent, participants will begin the trial.
- The parents will complete the Baseline questionnaire and provide the Baseline height and weight measurements of the children. The children will complete the Baseline cognitive assessments.
- After the baseline data collection, participants will be randomly allocated into the intervention or placebo study group. The participants and Citruslabs will not be informed who is in the intervention or the placebo group.
- The children will take 1 one scoop of the powder mixed with 6-8 oz of water, milk, or smoothies every morning.
- Parents will complete questionnaires at the end of Month 1, Month 2, Month 3, Month 4, Month 5, and Month 6.
- Parents will provide height and weight measurements of the children at Month 2, Month 4 and Month 6.
- The children will repeat the cognitive assessments at the end of Month 6.
- Completion of the Month 6 measurements marks the end of the study.

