6.6 COGNITIVE BATTERY TESTING

All children will complete cognitive assessments at the following time points:

- Baseline
- Month 6

The tests included are as follows:

Double Trouble - 1:30 timed test

 Based off of a classic Stroop test, Double Trouble measures selective attention, processing speed, and the brain's ability to focus on specific information when presented with conflicting and layered stimuli

Feature Match - 1:30 timed test

 Feature Match is a focus and processing task that requires surveying an increasingly difficult array of information and rapidly assessing the correct response while holding previously processed and detailed information in attention

Grammatical Reasoning - 1:30 timed test

Grammatical Reasoning is a deductive reasoning task that requires quickly interpreting
phrases and making logical conclusions from understanding. Variation between text and
shapes on screen require holding key information in short-term memory in order to
properly complete the task, leveraging the same parts of the brain that enable an
individual to remain focused between varied stimuli.

Digit Span - performance-based test (3-4 min)

Increasing in length after each successful attempt, Digit Span requires users to focus
on displayed numbers, hold them in short-term memory, and repeat them back correctly,
thereby showing cognitive flexibility and the brain's ability to perform memory and
attention related tasks without error

Token Search - performance-based test (3-4 min)

Leveraging the brain's executive functioning skills, Token Search requires participants
to hold information in working memory and remain focused on completing sequential
steps without making mistakes. The tasks become increasingly difficult, requiring more
active utilization of brain regions associated with processing, attention, and memory as
the task continues.

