7 STATISTICAL CONSIDERATIONS

Following data collection and the completion of the trial, the data will be analyzed by Citruslabs to determine the effect of the intervention versus the placebo. Between-arm and participant repeated measures between time point statistical tests will be used to examine differences in health outcomes during the study and compared to the placebo. Percentages of people who experienced improvements will also be examined. The analysis will adopt an intent-to-treat (ITT) approach, reflecting the primary objective of assessing the effectiveness of the test product as it would be used in the general population, inclusive of all randomized participants, irrespective of adherence or protocol deviations.

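### Section 6.4 does not separate stopping product from leaving the study, so a child given a new drug or antibiotics is likely to have no Month 6 cognitive score for the ITT analysis

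*Combined protocol and SAP*

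**What the plan says.** Section 6.4 opens its list of reasons with "An investigator may discontinue or withdraw a participant from the study for the following reasons". Stopping and withdrawing both refer to the study, and there is no separate route for stopping product alone. The reasons include "Significant study intervention non-compliance" and a disease course that requires product to be stopped. The last item is firmer than the opening line: "Participant should be withdrawn from the study if they start on a new drug or receive antibiotics". At withdrawal the section provides for recording the reason on a case report form. Children who leave after receiving product are not replaced.

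On the primary endpoint, Section 6.6 says "All children will complete cognitive assessments at the following time points" and lists Baseline and Month 6. Section 6.1 agrees: "The children will repeat the cognitive assessments at the end of Month 6". There is no cognitive test in between.

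Section 7 adopts an intent-to-treat analysis, "inclusive of all randomized participants, irrespective of adherence or protocol deviations". It names no method for missing scores. Section 3 measures immune function, a secondary endpoint, by how often the child has been ill.

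**The concern.** A rule in Section 6.4 appears to remove outcomes that the analysis in Section 7 needs. The trigger is broad: any new drug or any antibiotic course during six months, with no limit on class or duration. Significant non-compliance is another listed reason to leave, yet adherence is exactly what Section 7 says will not affect inclusion.

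If only the remaining children are analyzed, the trial estimates the effect in children who stayed, not in all who were randomized. Children who need treatment for an illness are not a random subset. The product is also meant to affect illness, so the two arms could lose different numbers and different kinds of children. Withdrawal would cut short the illness, height and weight data of the same children. Voluntary dropout leaves a similar gap, but this part is created by the protocol and can be avoided.

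**Working it through.** **The texts side by side**

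1. Section 6.4: a new drug or antibiotics should lead to withdrawal from the study. Only the reason is recorded, and no early-termination or later test is planned.
2. Sections 3, 4.1, 6.1 and 6.6: cognition is tested at Baseline and Month 6 only. A child who leaves in between and is not brought back has no post-baseline primary score.
3. Section 7: all randomized children are to be analyzed whatever their adherence.

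Items 1 and 2 together are likely to remove scores that item 3 requires. No other section provides follow-up after withdrawal.

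**The plan's own figure**

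Section 5.4 gives 60 children, 30 per arm. This cannot be reproduced, because the documents state no significance level, power, effect size, SD or dropout rate. The calculation below is therefore an illustration on assumptions.

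**Inputs**

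- From the plan: n = 30 per arm.
- Assumed: two-sample t-test on one cognitive score, two-sided 5%, SD = 1.
- Assumed: w = share withdrawn, equal in both arms and unrelated to outcome; 10% to 40%, with the rule fully enforced.
- Assumed: r = share of the effect kept by a child who stops product; 0, 0.5 or 1.
- Reference effect: d = 0.7356 SD, the difference that 30 per arm detects with 80% power. The normal approximation gives (1.960 + 0.842) × √(2/30) = 0.72; the t-test gives 0.74.

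**Formulas**

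- Remaining per arm: 30(1 − w)
- ITT effect: 0.7356 × (1 − w + wr)
- Overstatement of the ITT effect by the remaining children: 1/(1 − w(1 − r)) − 1
- Power: noncentral t, noncentrality effect × √(n/2), 2n − 2 degrees of freedom

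At w = 20%, 12 of 60 children have no Month 6 score and 24 per arm remain. With r = 0 the ITT effect is 0.7356 × 0.8 = 0.59 SD and the overstatement is 1/0.8 − 1 = 25%. With r = 0.5 the overstatement is 1/0.9 − 1 = 11%. With r = 1 it is zero.

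| w | Left per arm | ITT effect, r=0 (SD) | Overstatement, r=0 | Overstatement, r=0.5 | Power, remaining only | Power, all kept, r=0 | Power, all kept, r=0.5 |
|---|---|---|---|---|---|---|---|
| 10% | 27 | 0.66 | 11% | 5% | 76% | 71% | 76% |
| 20% | 24 | 0.59 | 25% | 11% | 70% | 61% | 71% |
| 30% | 21 | 0.51 | 43% | 18% | 64% | 50% | 66% |
| 40% | 18 | 0.44 | 67% | 25% | 57% | 39% | 61% |

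With r = 1, power with all children kept is 80% in every row. The two approaches have equal power when about 41% to 47% of the effect is kept. Below that, keeping all children gives less power.

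The percentages measure only the gap between two target effects when withdrawal is random. They do not include bias from illness-related or arm-related selection.

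**The case against.** The strongest reply is that the plan never says data collection stops. The opening line of Section 6.4 is permissive, and Section 6.6 refers to all children. A reader might infer that every such child certainly loses the Month 6 score. The documents do not support that: it is an inference from the ordinary meaning of leaving a study. It remains the likely outcome, since nothing arranges to test a child who has left. If enforcement is discretionary, the losses also become inconsistent.

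The rule has an understandable basis. The product contains a probiotic (Section 6.2), digestion is an endpoint, and Section 2.2 warns that dairy can interact with medications and asks for a 4-hour gap. These are reasons to stop product, manage its timing or record the event. They are not reasons to forgo a cognitive test.

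A reader might also take the larger percentages as an estimate of bias in this trial, or as bias in favor of the product. The documents support neither. The 67% needs 40% withdrawn, full enforcement and no retained effect, which is extreme for a child who may have taken product for months.

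Finally, the lack of a missing-data method in Section 7 is a separate omission. It would exist without the antibiotic rule, and this point does not depend on it.

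**Conclusion.** The point holds as a conflict between sections. Section 6.4 gives only one exit, and its new-drug and antibiotic item is likely to leave children without the primary outcome that Section 7's analysis requires. This should be fixed. Confidence is high on the textual conflict and low on any size.

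The direction and amount of selection bias cannot be fixed from the documents. The 25% to 11% overstatement at 20% withdrawn is an illustration that assumes random withdrawal, full enforcement and at most half of the effect retained; with full retention there is none.

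A reader might infer that keeping these children would raise power. That is not assured: if little of the effect is retained, power falls. The higher power under the present rule belongs to a different effect from the one Section 7 names.

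**What to change.** Change the Section 6.4 opening line and all of its items, not only the last, so that they are reasons to stop product at clinical discretion. Changing one item alone would leave the others as exits from the study. Suggested text:

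> A child who meets any of the following may stop product at clinical discretion but remains in the study. Questionnaires, height, weight and the Month 6 cognitive battery continue for every randomized child, unless consent or assent is withdrawn or continued assessment is not in the child's interest. New drugs and antibiotics are recorded with dates. Children who stay on product keep it at least 4 hours apart from medications.

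Add a sentence to Section 7 saying that scores obtained after product is stopped are included in the ITT analysis.

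The cost is two short text changes and a little more follow-up. Test time for the battery is 3 × 1.5 minutes plus 2 × 3 to 4 minutes, or 10.5 to 12.5 minutes, at home on the family's device. The scale and stadiometer are already supplied. The downside is possible dilution. With no retained effect, power at the 0.74 SD reference is 61% against 70% at 20% withdrawn, and 39% against 57% at 40%. The loss is smaller if children stay on product or retain part of the effect.

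### Withdrawing children who start a new drug or antibiotics drops the triggering illness from the Month 6 illness count: both arms can appear to improve, and the completers' arm comparison can be distorted in either direction

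*Combined protocol and SAP*

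**What the plan says.** - **Endpoint (Section 3).** A secondary endpoint is increased immune "function (assessed via the number of times the child has been ill in the past 6 months"). The questionnaire timepoints are "Baseline, Month 1, Month 2, Month 3, Month 4, Month 5, Month 6". The questionnaire itself is not in the documents.
- **Withdrawal (Section 6.4).** "Participant should be withdrawn from the study if they start on a new drug or receive antibiotics". This is withdrawal from the study, not only from product. The list containing it opens with "An investigator may discontinue or withdraw a participant from the study for the following reasons", so the lead-in permits what the bullet directs.
- **Record (Section 6.4).** "The reason for participant discontinuation or withdrawal from the study will be recorded on a Case Report Form (CRF").
- **Replacement (Section 6.4).** The plan treats two groups differently. For children who never start product, it says: "Participants who sign the informed consent form but do not receive the study intervention may be replaced". A child withdrawn after starting product is not replaced.
- **Completion (Section 4.4).** It requires the Month 6 questionnaire and the other last assessments.
- **Analysis (Section 7).** "Between-arm and participant repeated measures between time point statistical tests will be used to examine differences in health outcomes during the study", with comparison to placebo. A responder summary is planned too: "Percentages of people who experienced improvements will also be examined". The approach is intent-to-treat in all randomized participants. No method is given for outcomes that withdrawn children do not have.
- **Entry filter (Sections 5.1 and 5.2).** Exclusion 7 covers major illness in the prior three months, exclusion 6 covers surgery or invasive treatment in the prior six, and inclusion 5 asks for general good health.

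**The concern.** The event that removes a child is closely tied to the outcome being counted. Two things follow when the rule is applied. The treated illness is absent from the Month 6 count, although the same kind of illness can be in the Baseline count. Children with higher illness risk are also more likely to leave.

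Nothing in the plan puts the illness back. The intent-to-treat sentence says who is analyzed, not what to do without a Month 6 count. The withdrawal form records a reason, and Section 1.3 lists adverse event review during the intervention, but neither is said to feed the illness count. Monthly questionnaires may catch some illnesses, but if they repeat the 6-month look-back, their answers overlap and reach back before Baseline.

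Section 7 plans change between time points and percentage improved, the two summaries that this mechanism pushes toward improvement without any product effect. Section 4.3 links the dose choice to marketing claims, so a one-arm statement about fewer illnesses is a realistic use. The same withdrawals also remove Month 6 cognitive scores, the primary endpoint.

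**Working it through.** **Inputs.** From the documents: 30 children per arm (Section 5.4), a 6-month count and the withdrawal rule. The plan gives no illness rate, share of illnesses treated, dropout rate, alpha or power, so it has no figure of its own to reproduce here. Assumed: mean m = 2 illnesses per 6 months; a share p = 5%, 10% or 25% triggering the rule; the rule always applied; risk between children gamma with shape k = 1, k = 2, or equal (k to infinity).

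**Model.** In the product arm, a multiplies the rate of triggering illnesses and b the rate of non-triggering ones; in placebo a = b = 1. A completer has no triggering illness.

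- Withdrawn = 1 - (1 + apm/k)^-k
- Completers' Month 6 mean = (1 - p)bm / (1 + apm/k)
- Completers' own Baseline mean, same true rate and no entry filter = m / (1 + pm/k) in placebo

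**A. No product effect, within child.** Dividing the last two expressions gives a proportional fall of p, whatever m and k. If exclusion 7 removed every such illness in the prior 3 months, the fall is 1 - (1 - p)/(1 - p/2); at 25% that is 1 - 0.75/0.875 = 14%. If the entry criteria together removed all of them over 6 months, it is 0. False improvement is the share of 40,000 simulated arms of 30 entrants with a significant fall on a two-sided 5% paired t-test (nominal 2.5%).

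| p | Placebo withdrawn | Fall, no filter | False improvement | Fall, exclusion 7 in full | False improvement |
|---|---|---|---|---|---|
| 5% | 9-10% (about 3 of 30) | 5% | about 4% | 2.6% | 3% |
| 10% | 17-18% (about 5) | 10% | 6-7% | 5.3% | 4% |
| 25% | 33-39% (10-12) | 25% | 13-19% | 14% | 6-8% |

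At 25%, 36-49% of completers improve and 22-29% worsen (30-44% and 24-33% with exclusion 7 in full). If only half of the triggers at 25% lead to withdrawal, the fall is 12.5% with 7-9% false improvement; with exclusion 7 in full it is 0 with 2-3%. The completers' comparison between arms gives 2.1-2.5% false benefit, so it is not biased here. For m from 1.5 to 3, placebo withdrawal is 7-14%, 13-26% and 27-53%.

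**B to D. True product effect, completers compared between arms.** Ranges run over k.

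| Case | True ratio at p = 5%, 10%, 25% | Completers' ratio |
|---|---|---|
| B: all illnesses cut by 30% (a = b = 0.7) | 0.70 throughout | 0.70-0.72, 0.70-0.74, 0.70-0.78 |
| C: only triggering illnesses halved (a = 0.5, b = 1) | 0.98, 0.95, 0.88 | 1.00-1.05, 1.00-1.09, 1.00-1.20 |
| D: only non-triggering illnesses cut by 30% (a = 1, b = 0.7) | 0.715, 0.73, 0.775 | 0.70 throughout |

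Worst B case (p = 25%, k = 1): the placebo mean is 0.75 × 2/1.5 = 1.00 and the product mean 0.75 × 0.7 × 2/1.35 = 0.78. The difference is 0.22 instead of 2 - 1.4 = 0.60, with 33% and 26% withdrawn. Across k, the B difference shrinks by 5-19%, 10-34% and 25-63%; the ratio is unbiased when risk is equal. In case D at 25%, the true difference is 0.45; completers show 0.45 with equal risk and 0.30-0.36 with shape 1-2.

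**Unequal treatment.** The arm comparison also moves if illness numbers are equal but the share treated differs. With m = 2 and 20% treated on placebo, 10% on product gives 0.9/0.8 = 1.125 with equal risk (1.23 with k = 2), and 30% gives 0.7/0.8 = 0.875 (0.81).

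**Check of the remedy.** The on-study rate, counting the triggering illness and using time to withdrawal, was simulated with 400,000 children per arm, p = 10% and 25%, and six risk distributions. A true 0.70 gave 0.698-0.704, case C's 0.875 gave 0.873-0.882, case D's 0.775 gave 0.771-0.777, and no effect gave 0.997-1.004.

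**The case against.** The strongest reply is that Section 7 sets out to compare the product with placebo. With no product effect and equal treatment rates, both arms fall alike, so the within-arm fall misleads only someone who ignores placebo. That limits the damage, but Section 7 also plans tests between time points and percentages improved, and does not bar reading them within an arm.

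Second, bias between arms needs a difference between the arms and is small against noise. In the worst uniform case it is 0.60 - 0.22 = 0.38, below one standard error (0.56 with all 30 per arm, 0.40 in completers). Case C needs a product that acts only on treated illness, which no section suggests. This stands as a limit on size.

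Third, every rate is assumed, and the largest figures come from 25%, which means losing a third or more of the placebo arm. How often the rule fires is unknown: the lead-in is permissive, Section 1.3 lists no review of new medication, and a new drug need not reflect a countable illness. This also stands.

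Fourth, the unseen questionnaire and withdrawal form might already collect what is needed, and a repeated-measures analysis could use monthly answers. Even so, no stated rule carries those answers into the endpoint, whose only stated window is six months.

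**Conclusion.** The concern holds. This is a stated rule that works against a stated endpoint, not merely missing detail. Under the assumed rates, completers' counts fall by 5% to 25% with no product effect, and by less or not at all to the extent that the entry criteria filter Baseline. One-arm false improvement rises from 2.5% to between about 4% and 19% without that filter. The arm comparison is unbiased with no effect and equal treatment rates. With a true effect it can be understated, hidden, reversed or exaggerated, depending on which illnesses the product affects.

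The size rests on an assumed illness rate, trigger share and risk spread, and on the rule being applied. The endpoint is secondary and its power is low. The plan should be changed, ideally before any child is withdrawn, because the illness details are best captured at that moment.

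**What to change.** 1. Ask at Month 1 for illnesses since first product, and at Months 2 to 6 for illnesses since the last questionnaire. Keep the 6-month look-back at Baseline only.
2. On the existing withdrawal form, record the triggering illness, its date and any other illness since the last questionnaire. Count them all.
3. Compare arms on illness rate from first product to withdrawal or Month 6, using a negative binomial model with a log person-time offset, in all randomized children who start product. Report never-starters by arm.
4. Report withdrawals under this rule by arm.
5. Do not present Baseline to Month 6 illness change, or percentage improved, among completers as evidence of benefit.
6. Preferably, let these children stop product but remain in follow-up where the parent agrees. Steps 1 to 5 work without this, but it fits the intent-to-treat statement and keeps Month 6 cognitive scores. If follow-up is complete, the Section 3 count can be kept, with time off product included.

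**Cost.** Section 3 must be edited because the endpoint becomes an on-study rate. One question is reworded, items are added to an existing form and analysis text is written. No children or visits are added, and only step 6 changes the Section 6.4 rule. Step 6 means continued contact with roughly 2 to 12 children per arm at a mean of 2 illnesses.

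At 30 per arm and p = 25%, the model's 95% interval covers 92-96%, its false-benefit rate is 2.0-3.9%, and power for a ratio of 0.70 is 19-37%. For gamma shape 1, shape 2 and equal risk, power is 20-37%, against 6-22% for a completers' t-test. The result is therefore supportive only.
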